Safety assessments (Sections 10.4 and 11))																		
Vital signs	Х	X	Х	Х	Х	Х	X	x	Х	Х	X	Х	х	X	Х	Х	Х	Х	Х
Physical examination								x								Х		х	х
ECG				Х				х				Х				Х		х	х
Urine pregnancy test		х		х		х		х		х		х		х		х		х	х

Trial ID: LP0162-1325	Date: 14-Aug-2018	Version: 4.0
		Page 23 of 169

Panel 3 Schedule of trial procedures: maintenance treatment period and follow-up (continued)

							N	[ainten	ance tr	eatme	nt perio	bd							FU1 ²
Visit	13	14	15	16	17	18	19	20	21	22	23	24	25	26	27	28	29	30 ¹	31
Week	18	20	22	24	26	28	30	32	34	36	38	40	42	44	46	48	50	52	66
Safety assessments (Sections 10.4 and 11))																		
Serum chemistry, haematology, and IgE		х		Х		х		х		х		х		Х		х		х	Х
Urinalysis				Х				Х				Х				Х		Х	Х
Pharmacokinetics						х												х	Х
ADA						х												х	Х
Adverse events	Х	Х	Х	Х	Х	Х	Х	Х	Х	Х	X	Х	Х	Х	Х	Х	Х	Х	Х
Other assessments (Section 10.5)																			
Skin swabs (S. aureus)																		х	
Skin swabs (microbiome) ⁵																		Х	
Serum biomarkers (small panel)						х												х	
Serum biomarkers (large panel) ⁵						х												х	
Photography ⁵		х		х		х		х		х		х		х		х		х	

1) Assessments also to be done at an early termination visit.

2) Subjects will have a safety follow-up (FU1) 16 weeks after last injection of IMP; this is considered the end of trial visit. For subjects who are enrolled into the long-term extension trial (conducted under a separate protocol [LP0162-1337, ECZTEND]), the end of trial visit will be the last visit in trial LP0162-1325 before transfer to the extension.

- 3) Subjects who meet the following criteria will be transferred to open-label treatment (tralokinumab 300 mg Q2W with optional use of TCS [Panel 4]):
 - Subjects with IGA=0 at Week 16: IGA of at least 2 and not achieving EASI75 over at least a 4-week period (i.e., over 3 consecutive visits).
 - Subjects with IGA=1 at Week 16: IGA of at least 3 and not achieving EASI75 over at least a 4-week period (i.e., over 3 consecutive visits).
 - Subjects with IGA >1 at Week 16: not achieving EASI75 over at least a 4-week period (i.e., over 3 consecutive visits).

The first injections of open-label treatment will be given at the visit in the maintenance period where the subject meets these criteria.

Trial ID: LP0162-1325	Date: 14-Aug-2018	Version: 4.0
		Page 24 of 169

4) The eDiary consists of (i) Eczema-related Sleep NRS, (ii) Worst Daily Pruritus NRS, (iii) Average Daily Pruritus NRS, (iv) PGI-B, and (v) PGI-S.

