- Placebo (4 mL) at baseline, then placebo (2 mL) Q2W.

Maintenance treatment period (Week 16 to Week 52)

Subjects achieving a clinical response at Week 16 will continue into maintenance treatment that will continue until Week 52.

Clinical response is defined as IGA of 0 or 1, or at least 75% reduction in EASI score from baseline (EASI75).

Subjects randomised to tralokinumab in the initial treatment period will be re-randomised 2:2:1 to one of the following Q2W maintenance regimens stratified by region and IGA response at Week 16 (IGA 0/1 or IGA >1):

- Tralokinumab 300 mg (2 mL) ('tralokinumab Q2W').
- Alternating dose administrations tralokinumab 300 mg (2 mL) and placebo (2 mL) ('tralokinumab Q4W').
- Placebo (2 mL).

Subjects randomised to placebo in the initial treatment period who achieve a clinical response at Week 16, defined by IGA of 0 or 1, or EASI75 will continue to receive placebo Q2W in the maintenance treatment period.

Transfer to open-label treatment

Subjects will be transferred from maintenance treatment to open-label treatment (tralokinumab 300 mg Q2W with optional use of TCS) if they meet the criteria listed below. Transfer to open-label may occur at any visit while the subject is in the maintenance treatment period but no earlier than Week 22.

Subjects with IGA=0 at Week 16:

• IGA of at least 2 and not achieving EASI75 over at least a 4-week period (i.e., over 3 consecutive visits).

Subjects with IGA=1 at Week 16:

• IGA of at least 3 and not achieving EASI75 over at least a 4-week period (i.e., over 3 consecutive visits).

Subjects with IGA >1 at Week 16:

• Not achieving EASI75 over at least a 4-week period (i.e., over 3 consecutive visits).

Subjects who are transferred to open-label treatment will continue their scheduled visit sequence.

Open-label treatment (Week 16 to Week 52)

Any subject that does not achieve the protocol defined clinical response at Week 16 will be treated with open-label tralokinumab 300 mg Q2W with optional use of TCS. The open-label treatment will extend to Week 52.

For selected countries

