12.1 Sample size

A total of 780 subjects will be randomised 3:1 to initial treatment in this trial (585 subjects in the tralokinumab arm; 195 subjects in the placebo arm). The sample size is chosen to ensure that sufficient safety information is collected and to ensure a sufficient number of responders are re-randomised to maintenance treatment.

The primary endpoints for initial treatment IGA 0/1 and EASI75 at Week 16 are to be evaluated hierarchically testing both hypotheses of no difference between active and placebo at the 5% significance level. The hypothesis for IGA 0/1 will be tested first; if significant, the EASI75 hypothesis will be tested.

For the endpoint IGA 0/1 at Week 16, a sample size of 780 subjects randomised at 3:1 will provide >99% power to detect a difference between the 2 arms of 30% for tralokinumab and 10% for placebo at a 5% 2-sided level of significance. For the endpoint EASI75 at Week 16 a sample size of 780 will likewise provide >99% power to detect a difference between tralokinumab and placebo at Week 16, assuming EASI75 response rates of 40% and 15%, respectively.

With an IGA response rate of 30% at Week 16, 175 IGA responders initially treated with tralokinumab are expected to enter the maintenance treatment period (70 subjects on tralokinumab Q2W, 70 subjects on tralokinumab Q4W, 35 subjects on placebo). Assuming IGA response rates at Week 52 of 80%, 50% and 5%, respectively for Q2W, Q4W, and placebo, the power to show a difference at the 4% significance level will be >99% between Q2W and placebo and >99% between Q4W and placebo.

With an EASI75 response rate of 40% at Week 16, 235 EASI75 responders initially treated with tralokinumab are expected to enter the maintenance treatment period (94 subjects on tralokinumab Q2W, 94 subjects on tralokinumab Q4W, 47 subjects on placebo). Assuming EASI75 response rates at Week 52 of 90%, 55% and 5%, respectively for Q2W, Q4W, and placebo, the power to show a difference at the 4% significance level will be >99% between Q2W and placebo and >99% between Q4W and placebo.

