12.3.7 Analysis of safety

The analyses of safety will be based on the safety analysis sets. The reporting of safety data will be presented separately for the initial treatment, the maintenance treatment, and the open-label treatment.

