12.3.7.1 Adverse events

AEs will be coded during the course of the trial according to Medical Dictionary for Regulatory Activities (MedDRA). AEs will be presented by preferred terms and primary system organ class (SOC).

Treatment-emergent AEs will be summarised, however, all AEs recorded during the course of the trial will be included in the subject data listings. An event will be considered treatment-emergent if started after the first use of IMP or if started before the first use of IMP (applicable if subject had a wash-out) and worsened in severity thereafter. The tabulations described in the following will only include the treatment-emergent events. In each of the tabulations, AEs will be defined by MedDRA preferred terms within primary SOC.

An overall summary of the number of treatment-emergent AEs, number (percentage) of subjects with any treatment-emergent AEs, SAEs, deaths, premature discontinuations from the trial due to AEs, treatment-related AEs and severe AEs will be presented.

The number of AEs and the number of subjects experiencing each type of AE will be tabulated by treatment group. The percentage of subjects with AEs in the initial treatment period will be compared between treatment groups by a chi-square test or Fisher's exact test (if expected cell count < 5).

The severity for each type of AE will be tabulated by treatment group.

The causal relationship to IMP for each type of AE will be tabulated by treatment group.

Related AEs are defined as AEs for which the investigator has not described the causal relationship to IMP as 'not related'. The number of related AEs and the number of subjects experiencing each type of related AE will be tabulated. The percentage of subjects with related AEs in the initial treatment period will be compared between treatment groups by a chi-square test or Fisher's exact test (if expected cell count <5).

SAEs and AESIs will be evaluated separately. A narrative for each SAE will be given. AESIs and AEs leading to withdrawal from trial will be tabulated and listed.

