#### Assignment of AEs to periods

An adverse event will be assigned to a given period (initial, maintenance, open-label or follow-up) if the start date is after the start date and before the end date of that period (see Section 6.8.2, Table 4).

For AEs with start day on the same day as the first dose was given, only AEs starting after the first dose was given will be considered treatment emergent and assigned to the initial treatment period.

AEs with start date on the same day as the first dose of maintenance treatment will be assigned to the initial or maintenance period depending on whether the AE started before or after the dose was given.

AEs with start date on the same day as the first dose of open-label treatment will be assigned to the previous treatment period (can be initial or maintenance) or assigned to the open-label period depending on whether the AE started before or after the dose was given.

AEs starting on the day of exposure end (as defined in Section 6.8.2) will be assigned to the last treatment period.

For handling of incomplete start dates of adverse events, see Section 6.8.3.

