#### Sort order of AE tables

Generally, AE tables by system organ class and/or preferred term will be sorted by decreasing number of affected subjects:

- For the initial treatment period, AE tables will be sorted by decreasing number of affected subjects in the Tralokinumab Q2W group.
- For the maintenance treatment period, AE tables will be sorted by decreasing total number of affected subjects in the Tralokinumab treatment groups (sum of Q2W and Q4W).
- For the entire treatment period, AE tables will be sorted by decreasing number of affected subjects in the "Tralokinumab total" group.

• For the follow-up period, AE tables will be sorted by decreasing total number of affected subjects in the Tralokinumab treatment groups (sum of Q2W, Q4W and Q2W+optional TCS).

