#### Trial periods

The time from exposure start to exposure end will be divided into initial period, maintenance period and open-label period, and remaining time after exposure end will be assigned to the follow-up period as shown in Table 4 (ADaM variable APHASE). The ADaM variable APERIODC will indicate the latest treatment (initial, maintenance or open-label) at any given time point, thus not including a follow-up period (Table 5).

Trial ID: LP0162-1325	Date: 20-May-2019	Version: 1.0
		Page 27 of 31

ADUASE	Start of pariod	End of noniad (only if star	t data a
Table 4: Start a	nd end time of trial	periods (ADaM variable APH	IASE).

APHASE	Start of period	End of period (only if start date exists)
Initial	Exposure start	Date and time (minus 1 second) of first maintenance
period		dose (if existing)
		else
		Date and time (minus 1 second) of first open-label dose
		(if existing)
		else
		Exposure end
Maintenance	Date and time of	Date and time (minus 1 second) of first open-label dose
period	first maintenance	(if existing)
	dose (if existing)	else
		Exposure end
Open-label	Date and time of	Exposure end
period	first open-label	
	dose (if existing)	
Follow-up	Exposure end	Date of safety follow-up visit (if existing) at time
period 	(plus 1 second)	23:59:00
		else
		Date of last contact at time 23:59:00

1) Only applicable if date of last contact is not equal to date of exposure end.

APERIODC	Start of period	End of period (only if start date exists)
Initial period	Exposure start	Date and time (minus 1 second) of first maintenance
		dose (if existing)
		else
		Date and time (minus 1 second) of first open-label dose
		(if existing)
		else
		Date of last contact at time 23:59:00
Maintenance	Date and time of	Date and time (minus 1 second) of first open-label dose
period	first maintenance	(if existing)
	dose (if existing)	else
		Date of last contact at time 23:59:00
Open-label	Date and time of	Date of last contact at time 23:59:00
period	first open-label	
	dose (if existing)	

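### Maintenance-period AE tables use counts and percentages alone, although follow-up stops at transfer to open-label and would probably be shorter on placebo

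*Protocol*

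**What the plan says.** Protocol 12.3.7 states: "The reporting of safety data will be presented separately for the initial treatment, the maintenance treatment, and the open-label treatment". Within each period, 12.3.7.1 specifies the AE output: "The number of AEs and the number of subjects experiencing each type of AE will be tabulated by treatment group". The overall summary there gives numbers and percentages of subjects, and a test is planned for the initial period only. SAP 6.7.1 says that AEs are summarised and listed, and adds rules for period assignment and sort order: "For the maintenance treatment period, AE tables will be sorted by decreasing total number of affected subjects". Neither document names an AE rate per unit of time or a time-to-event AE summary.

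An AE belongs to a period "if the start date is after the start date and before the end date of that period" (SAP 6.7.1). In SAP Table 4 (6.8.2) the maintenance period ends at "Date and time (minus 1 second) of first open-label dose", or at exposure end if there is no such dose. Panel 3, footnote 3 (Protocol Section 4) fixes when that dose is given: "The first injections of open-label treatment will be given at the visit in the maintenance period where the subject meets these criteria". The criteria in Protocol 7.1 depend on the Week 16 IGA. For IGA=1, for example, the criterion is "IGA of at least 3 and not achieving EASI75 over at least a 4-week period". All three require loss of EASI75 over three consecutive visits, and transfer cannot occur before Week 22.

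Several planned outputs bear on this: days of exposure by group (Protocol 12.3.3.1), patient-years of exposure (PYE) per period (SAP 6.5), and reasons for leaving the treatment arm by last visit (Protocol 12.3.1).

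**The concern.** Time at risk in the maintenance AE tables depends on keeping response, and the plan expects response to differ sharply by arm: "Assuming EASI75 response rates at Week 52 of 90%, 55% and 5%, respectively for Q2W, Q4W, and placebo" (Protocol 12.1). Subjects re-randomised to placebo would probably transfer more often and sooner, and their later AEs move to the open-label tables. A crude percentage, or a raw event count per subject, then falls for a reason unrelated to risk. At equal hazard the order would be placebo lowest, Q4W in between and Q2W highest.

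The error runs against the drug and hides no harm. It could still mislead a reader who compares the two regimens, and Protocol 5.4 raises whether less frequent dosing is sufficient. AE/SAE frequency is an 'other' maintenance endpoint (Protocol 6.2), so no confirmatory test, estimand or type 1 error is involved.

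**Working it through.** **The plan's own figures.** It states no maintenance AE percentage or follow-up time. Its arm sizes can be checked: 585 × 0.40 = 234 (stated as 235), split 2:2:1 into 94/94/47. Its power above 99% for the maintenance comparisons is also reproduced at a two-sided 4% level.

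**Inputs from the documents.** Maintenance lasts 36 weeks with no transfer in the first 6 (Protocol 7.1). Week 52 EASI75 rates r are 0.90/0.55/0.05 and n is 94/94/47 for Q2W/Q4W/placebo (12.1). A year is 365.25 days (SAP 6.5).

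**Cap on transfer.** Every transferred subject counts as a Week 52 non-responder (12.3.6.1). At the planning rates, at most 10/45/95% can therefore transfer, about 9/42/45 subjects. The true share should be lower: rescue and missing data also count as non-response, and subjects with IGA=1 at Week 16 must also reach an IGA of at least 3.

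**Assumptions.** A share f of planned non-responders transfers, so T = f(1 − r). Transfer is either exponential or evenly spread over Weeks 22 to 52. The first-AE hazard is the same in all arms, 1 per patient-year, so λ = 7/365.25 = 0.01917 per week.

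**Formulas.**
- Exponential: μ = −ln(1 − T)/30; weeks at risk = 6 + T/μ; crude risk = 1 − e^(−6λ) + e^(−6λ) · λ/(λ+μ) · (1 − e^(−30(λ+μ))).
- Even: weeks at risk = 6 + 30(1 − T/2); crude risk by numerical integration.
- SE of a gap = √[p₁(1 − p₁)/n₁ + p₂(1 − p₂)/n₂].

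**Worked case: f = 1, exponential.**
- Placebo: T = 0.95, μ = 0.0999, weeks = 6 + 0.95/0.0999 = 15.5. Crude risk = 0.1086 + 0.8914 × 0.1610 × 0.9719 = 24.8%.
- Q2W: T = 0.10, μ = 0.00351, weeks = 34.5, crude risk 48.0%.
- Gap 23.2 points; SE = √(0.480 × 0.520/94 + 0.248 × 0.752/47) = 8.1 points.

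**All cases at 1 per patient-year (Q2W/Q4W/placebo).**

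| f | Timing | Weeks at risk | Crude % | Q2W − placebo (SE) | Q2W − Q4W |
|---|---|---|---|---|---|
| 0.25 | exponential | 35.6/34.3/32.3 | 49.4/47.8/45.4 | 4.0 (8.9) | 1.6 |
| 0.25 | even | 35.6/34.3/32.4 | 49.4/47.9/45.7 | 3.7 (8.9) | 1.5 |
| 0.5 | exponential | 35.2/32.5/28.1 | 48.9/45.7/40.5 | 8.5 (8.8) | 3.3 |
| 0.5 | even | 35.2/32.6/28.9 | 49.0/45.9/41.5 | 7.5 (8.8) | 3.1 |
| 1 | exponential | 34.5/28.6/15.5 | 48.0/41.0/24.8 | 23.2 (8.1) | 7.0 |
| 1 | even | 34.5/29.25/21.75 | 48.1/41.9/33.1 | 15.0 (8.6) | 6.2 |

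The SE of the Q2W − Q4W gap is about 7 points. Events per 100 patient-years are 100 in every arm and every row.

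**Sensitivity.**
- Hazards of 0.5 to 2 per patient-year give Q2W − placebo gaps of 2.4 to 5.0 (f = 0.25), 4.8 to 10.7 (f = 0.5) and 9.5 to 30.4 points (f = 1).
- At 1 per patient-year the gap passes 1.96 SE only if about 85% or more of planned non-responders transfer with exponential timing, and never with even timing.
- The IGA planning rates (80/50/5%, n = 70/70/35) give 3.5/3.3, 7.6/6.6 and 21.4/13.2 points (exponential/even) for f = 0.25, 0.5 and 1.

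**When the rate misleads.** Take an identical front-loaded hazard in all arms: 2 per patient-year for 12 weeks, then 0.5. With full transfer, events per 100 patient-years are 102/111/152 (exponential) or 102/110/129 (even), against crude 49/45/36% or 49/46/41%.

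**The case against.** **The tables may already include a rate.** Protocol 12.3.7.1 is not the full table list, since the SAP's sort rules name AE tables for the entire treatment period and for follow-up. PYE may have been defined with AE rates in mind. That is possible, but neither document says so.

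**Equal hazard may be wrong.** Clinically significant worsening of any condition is reportable as an AE (Protocol 11.5.6), so subjects losing response on placebo may have more AEs before transfer. At 1 per patient-year on active treatment, a placebo hazard ratio of about 1.13 (f = 0.25) or 1.3 (f = 0.5) would close the Q2W − placebo gap; f = 1 needs about 1.7 to 2.4. The direction of the observed gap is therefore uncertain. This stands, but it does not remove the shortfall caused by shorter follow-up. It means that a higher placebo risk would be masked.

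**The gap is mostly within chance error, and the inputs for a rate are planned.** Both are true. The Q2W − Q4W gap is at most about one SE. A reader could see the imbalance in the exposure outputs and divide, but would have to repeat this for each preferred term.

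**Rates are imperfect too.** A front-loaded hazard distorts them in the drug's favour, and follow-up that ends on disease worsening is informative, which a rate does not correct. This also stands. It argues for showing both measures, not for crude figures alone.

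**Conclusion.** The point holds, as a low-cost improvement and not a flaw in any confirmatory analysis. Maintenance AE results are specified as counts and percentages over follow-up whose length depends on keeping response. On the plan's own response rates, placebo would probably have the shortest follow-up.

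The true size is unknown because the documents give no transfer share, timing or AE hazard. With an equal constant hazard of 1 per patient-year, the Q2W-minus-placebo distortion is about 4 points if a quarter of planned non-responders transfer and 7.5 to 8.5 if half do. The 15 to 23 points at full transfer are a cap that is unlikely to be reached. Most of this range lies within chance error at 94/94/47 subjects, and it errs against the drug.

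**What to change.** In SAP 6.7.1, for the maintenance-period AE, SAE and AESI tables, add events per 100 patient-years by treatment group, using the PYE of SAP 6.5, and keep the crude counts and percentages. State that the two are read together: crude percentages fall with shorter follow-up, while rates per patient-year assume a roughly constant hazard.

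The cost is one sentence and one table column, since AEs and PYE can both use the Table 4 periods. The drawback to state is that, if AEs cluster early, the rate overstates placebo risk and makes tralokinumab look safer. The crude figures must therefore stay in the table.

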12.3.10 General principles

Unless otherwise stated, all significance tests will be two-sided using the 5% significance level. All CIs will be presented with 95% degree of confidence.

An observed-cases approach will be used for tabulations of data by visit (i.e. involving only those subjects who attended each specific visit).

Trial ID: LP0162-1325	Date: 14-Aug-2018	Version: 4.0
		Page 114 of 169

Categorical data will be summarised using the number and percentage of subjects in each category and treatment group. Continuous data will be summarised using the mean, median, standard deviation, minimum and maximum values.

All the analyses specified in the protocol will be reviewed in relation to the blinded data actually obtained and the statistical analysis plan update will be finalised before breaking the randomisation code.

Any changes from the statistical analysis planned in this clinical trial protocol will be described and justified in a protocol amendment, the statistical analysis plan update and/or in the CTR dependent on the type of deviation.

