# 6.7 Analysis of Safety

#### 6.7.1 Adverse Events

Adverse events will be summarised and listed.

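### Between-arm comparison of adverse events is planned as a p-value only; add risk differences with 95% confidence intervals for the initial period and say whether the test is overall or per term

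*Protocol*

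**What the plan says.** Protocol 12.3.7.1 tabulates numbers and percentages of subjects with AEs by treatment group. It then adds one inferential step, for AEs and again for related AEs: the percentage of subjects "in the initial treatment period will be compared between treatment groups by a chi-square test", or by Fisher's exact test where an expected cell count is below 5. SAEs and AESIs are evaluated separately, with narratives for SAEs and tables and listings for AESIs and for AEs leading to withdrawal.

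SAP 6.7.1 opens with "Adverse events will be summarised and listed" and otherwise covers the assignment of events to trial periods and the sort order of tables. It adds no estimate or interval.

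The general rule in protocol 12.3.10 is "Unless otherwise stated, all significance tests will be two-sided using the 5% significance level". The same section sets 95% as the level of any CI that is presented, but it does not call for one on AEs.

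On sample size, protocol 12.1 says "The sample size is chosen to ensure that sufficient safety information is collected", with "585 subjects in the tralokinumab arm; 195 subjects in the placebo arm". It gives no AE difference that this number of subjects could detect or exclude.

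**The concern.** Safety and tolerability over 16 weeks is a stated objective (protocol 6.1), and the initial period is the trial's randomised placebo comparison of all enrolled subjects. The only between-arm inference planned there for AEs is a test of no difference. A p-value does not give the size of the difference or the range of differences compatible with the data. With 195 placebo subjects that range can be wide for uncommon events.

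The efficacy plan is fuller. The primary binary endpoints get a treatment estimate with a 95% CI (protocol 12.3.5.1.1). For AEs the reader would see two percentages and a p-value.

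A second gap is scope. The text does not settle whether the test is run on two overall percentages (any AE, any related AE) or for each preferred term. The preceding sentence deals with each type of AE, and the Fisher fallback for small counts points to per-term use. The literal wording of the comparison points to the overall percentages.

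**Working it through.** **Inputs.** Arm sizes 585 and 195 (protocol 12.1); two-sided 5% (12.3.10); chi-square, or Fisher's exact test if an expected cell count is below 5 (12.3.7.1). I take this as the smallest expected cell, and the chi-square as uncorrected for continuity, which the protocol does not specify. The analysis uses exposed subjects (SAP section 5), so these are the planned maximum numbers. All AE rates below are assumptions.

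**Step 1: reproduce the plan's own power.** Protocol 12.1 states that 780 subjects "will provide >99% power to detect a difference between the 2 arms of 30% for tralokinumab and 10% for placebo", and likewise for EASI75, "assuming EASI75 response rates of 40% and 15%, respectively". Normal approximation: power = Φ[(d − 1.96·SE0)/SE1], with SE0 = √[p̄(1−p̄)(1/585 + 1/195)] and SE1 = √[pT(1−pT)/585 + pC(1−pC)/195].

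- IGA 0/1: p̄ = (0.30×585 + 0.10×195)/780 = 0.25; SE0 = 0.0358; SE1 = 0.0286; (0.20 − 0.0702)/0.0286 ≈ 4.53; power 99.9997%.
- EASI75: p̄ = 0.3375; SE0 = 0.0391; SE1 = 0.0326; (0.25 − 0.0766)/0.0326 ≈ 5.31; power above 99.9999%.

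Both agree with the stated figure of more than 99%.

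**Step 2: the same formula at 1% versus 3%.** p̄ = 0.025; SE0 = 0.0129; SE1 = 0.0100; (0.02 − 0.0253)/0.0100 ≈ −0.53; power 29.8%. The expected placebo count is 0.025×195 = 4.9, at the edge of the Fisher rule, so an exact calculation is needed.

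**Step 3: exact power under the protocol's rule.** Sum the two binomial probabilities over all tables in which the test selected by the rule gives p ≤ 0.05.

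| Placebo vs tralokinumab (assumed) | Power | Missed |
|---|---|---|
| 1% vs 3% | 27.6% | 72.4% |
| 3% vs 6% | 35.7% | 64.3% |
| 2% vs 5% | 43.9% | 56.1% |
| 5% vs 10% | 59.7% | 40.3% |
| 2% vs 6% | 65.7% | 34.3% |
| 60% vs 70% (any AE) | 72.8% | 27.2% |
| 1% vs 5% | 80.0% | 20.0% |
| 10% vs 20% | 92.3% | 7.7% |

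At 1% versus 3% Fisher's test is selected in about 51% of realisations. Using one test throughout gives 26.4% (Fisher) or 30.2% (uncorrected chi-square); a continuity-corrected chi-square gives 16.9%.

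**Step 4: what an interval would show.** Take 18/585 (3.1%) versus 2/195 (1.0%), close to the expected counts at 3% and 1%. The smallest expected count is 20×195/780 = 5.0, so the rule selects chi-square: 780×(18×193 − 2×567)²/(585×195×20×760) = 2.46, p = 0.12 (Fisher would give 0.19). The risk difference is 3.08% − 1.03% = 2.1 points, Newcombe (score-based) 95% CI −0.8 to 3.9. The p-value reports no significant difference; the interval shows that an excess of almost 4 points is still compatible with the data.

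The simple Wald interval for the same table is 0.1 to 4.0 points. It excludes zero although the test does not reject, which is why the interval type matters for sparse events.

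For scale, with equal true rates the approximate half-width is 1.96·√[p(1−p)(1/585 + 1/195)]: 2.3 points at p = 2% and 3.5 points at p = 5%.

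**The case against.** The strongest reply is that the safety plan is descriptive. Its endpoint is the frequency of AEs and SAEs by term. It also has SAE narratives, AESI tables, laboratory shift tables and clinical-significance thresholds, ECG shift tables, ADA associations and an independent DMC with its own analysis plan. Counts and percentages by arm are tabulated, so a reader can see the point difference and compute a crude interval. This stands in part: what is missing is a pre-specified, displayed interval, not the underlying data.

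Three stronger readings are tempting, and the documents do not support them.

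- A reader might infer that the sponsor means to treat p > 0.05 as evidence of safety. Neither document says so.
- A reader might take the 72% miss rate as a property of the planned test. It rests on assumed rates, and power reaches 80% at 1% versus 5% and 92% at 10% versus 20%. The documents set no power target for safety against which to call any of these a failure. If the test is for overall percentages only, the low-rate scenarios do not describe a planned test at all.
- A reader might object that the test ignores region and baseline IGA. Randomisation is 3:1 within those strata, so pooled percentages should be close to balanced, and no consequence has been shown. Weighting rare events over six strata (three regions by two IGA levels) has its own difficulties.

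It is also fair to say that an interval adds no information beyond what 195 placebo subjects provide. It only makes the uncertainty visible.

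**Conclusion.** The point holds as a cheap improvement to reporting and does not threaten the trial's validity. The planned between-arm inference for AEs and related AEs is a bare p-value, and no risk difference or CI is planned for any AE, SAE or AESI.

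If the test is per preferred term, it is weak for uncommon events, with power from about 28% (1% versus 3%) to 80% (1% versus 5%) over the low-rate scenarios examined. If it is overall only, power is about 73% at 60% versus 70%, and individual events and AESIs receive no between-arm inference. Under either reading, a non-significant result alone leaves unstated how large an excess remains possible.

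The power figures depend on the assumed rates, on the planned arm sizes being reached in the safety set, and on an uncorrected chi-square. The absence of an estimate and interval depends on none of these.

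**What to change.** In protocol 12.3.7.1 and SAP 6.7.1:

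- Present the tralokinumab minus placebo risk difference with a 95% CI for the initial period, for any AE, related AEs, SAEs, each AESI and the common preferred terms. Use a score or exact type of interval where events are sparse, and define "common" by a stated frequency threshold.
- State whether the chi-square or Fisher test applies to overall percentages or to each preferred term.
- State that any retained p-values are descriptive. Weighting by region and baseline IGA is optional.

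The data are already collected, and design, sample size and clinical management do not change. The cost is SAP wording and one more table column. The downside is that intervals for uncommon events will be wide.
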